## **Protocol Synopsis**

**Title:** Effects of IV Omadacycline on Gut Microbiome

**Version:** 2.0

**Protocol Number:** 001

**Version Date:** 24APR2023

**Principal investigator:** [name]

**Accrual Target:** 8 participants

**Population:** Healthy participants between ages 18 and 40 years.

**Regimen:** Participants will receive a 10-day course of omadacycline with 5 days of intravenous therapy followed by 5 days of oral therapy.

**Study Duration:**

Length of study: Approximately 12 months from First Participant First Visit to Last Participant Last Visit.

Length of participation of study participants: Up to 36 days.

## 1.0 STUDY OBJECTIVES

### 1.1.1 Primary Objective:

To characterize the impact of 5 days of IV omadacycline followed by 5 days of oral omadacycline on the gut microbiome of healthy volunteers.

## 2.0 BACKGROUND AND SCIENTIFIC RATIONALE

*Clostridioides difficile* infection is a major health threat in the United States that is most often an outcome of perturbation of gut microbiota following antibiotic use [1]. Even the limited number of antibiotic regimens effective in the treatment of *C. difficile* infection have the ability to impact gut microbiome in a negative way and may increase the risk of relapse due to such perturbations [2,3,4]. Thus, there is an increasing need to identify candidate therapies for *C. difficile* that target this pathogen but have minimal effect on the native gut microbiome.

Omadacycline is an aminomethylcycline tetracycline antibiotic that is approved by the US Food and Drug Administration (FDA) for the treatment of community-acquired bacterial pneumonia (CABP) and acute bacterial skin and skin structure infections (ABSSSI) [5]. A recent study demonstrated *in vitro* activity of omadacycline against *C. difficile* [6].

Given the clinical need to improve upon current antibiotic regimens for the treatment of *C. difficile* infection with a particular focus on the impact of therapies on gut microbiome, we propose this study to characterize the impact of IV omadacycline on gut microbiome of healthy volunteers. We plan to enroll healthy volunteers between the ages of 18 and 40 years old and without history of cardiovascular, gastrointestinal, hepatic, or renal disease to receive 5 days of intravenous omadacycline followed by 5 days of oral omadacycline.

### 2.1 Reproductive and Developmental Toxicity

Based on animal data, there is reasonable suspicion that omadacycline has the potential to cause fetal harm [5,7]. We will only enroll females of childbearing potential who are not pregnant at baseline and who agree to use a reliable method of birth control or remain abstinent. Additionally, females of childbearing potential who use hormone-based oral contraceptives (OCs) will be required to use a second form of birth control (e.g. condom) because of a possible drug interaction with omadacycline which may lower the effectiveness of OCs.

### 3.0 PATIENT SELECTION

#### 3.1 Selection Criteria

#	Yes	No	Inclusion Criteria
1			Is aged 18-40 years.
2			Is willing and able to comply with all study procedures including providing informed consent, and visiting the ID Clinical Trials Center at Wake Forest Baptist Medical Center at the specified times to receive study medication and/or to deliver samples (must have reliable transportation).
3			Is considered healthy, without history of cardiovascular, gastrointestinal, hepatic, or renal disease.
4			Meets one of the three categories below:   1. Is female and of child bearing potential and agrees to use highly effective contraception during the study and for at least 7 days after the last dose of study product  2. Is female and not of child bearing potential due to (One must be checked):  surgical sterility OR  congenital sterility OR  post-menopausal state OR  pre-menarchal state
#	Yes	No	Exclusion Criteria
1			Has consumed probiotics within 30 days prior to enrollment.*
2			Has consumed antibiotics within 90 days prior to enrollment.*
3			Has a known hypersensitivity to omadacycline or tetracycline-class antibacterial drugs.
4			Is pregnant or breastfeeding.
5			In the opinion of the investigator, is experiencing signs or symptoms of acute illness that increase the risk of adverse effects from participating in the study.
6			Has previously participated in the study.

\*Potential study volunteers who are excluded due to probiotic or antibiotic consumption may be re-screened at a later date when outside the exclusionary window(s).

Investigator Signature	
Date of Signature (DDMMYY YYYY)	

### **3.2 Sample Size**

The study will enroll 8 participants.

## **4.0 INVESTIGATIONAL PLAN**

### **4.1 Screening**

After signing informed consent, participants will undergo a brief interview about medications taken within the last 90 days with a particular focus on probiotic and antibiotic use. Volunteers who have received probiotics in the past 30 days and volunteers who have received antibiotics within the past 90 days will not be considered for participation. Participants will also undergo a limited review of their medical history to capture cardiovascular, gastrointestinal, renal, and hepatic diagnoses or conditions. Once the investigator confirms that the participant meets all patient selection criteria, the investigator and study team will schedule the patient's first dose to occur on study Day 1. If dosing is to occur immediately, the participant will provide a stool sample directly following informed consent but before omadacycline dosing. If dosing is to occur on a subsequent day, the participant will bring a stool sample (obtained the morning of Day 1) to the clinic prior to dosing or will provide the sample in clinic just prior to Day 1 dosing. The screening period will begin no more than 5 days before study drug administration on study Day 1.

### **4.2 Omadacycline dosing:**

Study Day	Dose	Route of administration and schedule
Day 1	200 mg	Intravenous, infused over 60 minutes
Days 2 – 5	100 mg	Intravenous, infused over 30 minutes
Days 6 – 10	300 mg	Oral, two tablets once daily (dispensed as ten 150 mg tablets)

Omadacycline powder will be provided by the sponsor, reconstituted with Sterile Water, and then further diluted for Injection under aseptic conditions as follows: 2 vials (200 mg) to 2 mg/mL, and 1 vial (100 mg) to 1 mg/mL. Each subject will receive 2 vials on day 1 followed by 1 vial on days 2-5 (4 additional vials). Subjects will then receive 2 oral tablets (300 mg) daily on study days 6 through 10 (5 days).

### **4.3 Monitoring subjects during omadacycline infusions**

During the first infusion of omadacycline, subjects will be monitored by either a research nurse or investigator. At a minimum, the monitor will be present with the subject during the first 10 minutes of the infusion and will return every 5-10 minutes or sooner thereafter for the remainder of the 60-minute infusion. The monitoring study team member will,

- Observe the general appearance of the subject
- Examine skin color for possible infusion reaction

- Examine the site of the infusion for possible redness or swelling
- Ask the subject if they are experiencing discomfort at the infusion site
- Ask the subject if they are experiencing any of the following symptoms: nausea, headache, dizziness, lightheadedness, fever, chills, shortness of breath, flushing, itching, or chest discomfort
- Report any symptoms to the investigator immediately, if investigator is not already present
- Along with investigator, assess the severity of any reported symptoms

The research nurse will perform and record vital signs for any clinically significant symptoms. Depending on the severity of any symptoms reported, the investigator will determine whether the infusion should be held or discontinued. If needed, the research nurse or investigator will activate the institution's code response system for "sudden illness" or "cardiac-pulmonary arrest".

If the subject tolerates the first infusion, subsequent infusions will be administered with less frequent monitoring. For these infusions, the monitoring research team member will be present with the subject for the first 5 minutes of the infusion and return every 10 minutes or sooner for the remainder of the 30-minute infusion. The same approach to monitoring will be undertaken (see methods above).

#### **4.4 Laboratory Samples**

Female participants of childbearing potential must produce a negative urine pregnancy test on Day 1 prior to dosing. Results from pregnancy tests performed within 3 days prior to Day 1 will be accepted for eligibility. Due to the teratogenic potential of omadacycline, a urine pregnancy test must be repeated and confirmed negative on Day 5 prior to infusion. Omadacycline dosing will be discontinued if the Day 5 pregnancy test is positive.

Participants will provide a total of 13 stool samples and 12 saliva samples during study participation. Two stool samples (one before and one after dosing) and one saliva sample will be provided on Day 1. On Days 2-10, Day 13 (+1), and Day 31 ( $\pm 1$ ) participants will provide the first stool sample of the day and one saliva sample per study day. Participants should deliver any home-collected stool samples to the clinic by 4:30pm on the day of collection and should store the sample in the refrigerator if not immediately bringing to the clinic. If the first stool sample of the day is collected after 4:30pm, it may be stored in the refrigerator overnight and delivered to the clinic the next morning.

## 4.5 Schedule of Events

	Screening (-5 or 1) I	Day 1	Day 2	Day 3	Day 4	Day 5	Day 6	Day 7	Day 8	Day 9	Day 10	Day 13 (+1)	Day 31 (±1)
Informed Consent	X												
Eligibility	X												
Enrollment	X												
Limited Medical History A	X												
Limited Medication History B	X												
Investigational Product													
Omadacycline IV 200 mg C		X											
Omadacycline IV 100 mg D			X	X	X	X							
Omadacycline Oral 300 mg							X	X	X	X	X		
Laboratory Assessments													
Stool Sample E,F	X	X	X	X	X	X	X	X	X	X	X	X	X
Saliva Sample		X G	X	X	X	X	X	X	X	X	X	X	X
Urine pregnancy test	X J					X J							
Safety Assessments													
Adverse Events		X	X	X	X	X	X	X	X	X	X	X	X
Concomitant Medications H		X	X	X	X	X	X	X	X	X	X	X	X

A History of cardiovascular, gastrointestinal, hepatic, or renal disease is exclusionary

B No probiotic consumption within 30 days of enrollment. No antibiotic consumption within 90 days prior to enrollment.

C Infused over 60 minutes

D Infused over 30 minutes

E All stool samples should be delivered to the clinic less than 24 hours after collection. Delivery will typically occur the same day as collection, but could be the following morning if the sample is collected after 4:30pm

F On all study days after Day 1, the first stool of every day should be the one collected

G The saliva sample on Day 1 should be provided before omadacycline dosing

H Assessment of antibiotic and probiotic use to occur at each study visit

I Re-screening is allowable

J Results from a recent pregnancy test (within 3 days prior to Day 1) will be accepted for eligibility determination. Pregnancy tests should be performed and confirmed negative prior to dosing on Days 1 and 5.

## 4.6 Setting

### 4.6.1 Recruitment and advertising

Advertisements will be posted on the campus of High Point University (HPU) in High Point, NC and Atrium Health Wake Forest Baptist (AHWFB) in Winston-Salem, NC. Study team members at HPU and AHWFB will manage recruitment.

### 4.6.2 Study procedures

Study procedures including informed consent, eligibility confirmation, medical and medication history review, investigational product dispensing and administration, data collection, safety monitoring, and sample collection, temporary storage, and shipment will take place in the Wake Forest University Health Sciences Infectious Diseases Clinical Trials Center (IDCTC) at the Winston-Salem, NC campus of Atrium Health Wake Forest Baptist.

### 4.6.3 Laboratory and Data Analysis

The [name] Lab at University of Houston College of Pharmacy in Houston, TX will perform laboratory and data analysis.

## 5.0 SUBJECT RECRUITMENT METHODS

Study team members at HPU and AHWFB will post advertisements, receive initial contact from interested study candidates, and perform pre-screening. The contact information of candidates who appear eligible based on pre-screening will be transferred to the staff of the IDCTC team for management of consent and consent process documentation, final sign-off on eligibility, and study enrollment.

## 6.0 ANALYTICAL PLAN

### 6.1 University of Houston Microbiome analysis:

#### *DNA extraction:*

Prior to DNA extraction, the OMNIgene tubes will be vortexed vigorously for at least 10 seconds. DNA will be extracted from the tube by aliquoting 300  $\mu$ L of the tube sample using the AnaPrep system DNA extractor (AnaPrep 2, BioChain Instruments, Newark CA) and the following protocol. Approximately 400  $\mu$ L of lysed bacteria will be mixed and loaded into the AnaPrep system and gDNA will be extracted using 400 microliter input volume and 100  $\mu$ L elution volume. DNA will be eluted in 100  $\mu$ L of buffer and concentration measured using a Nanodrop 2000 (Fisher Scientific, Waltham, MA). If the DNA concentration is less than 10  $\mu$ g/mL, the extraction will be repeated. A 50  $\mu$ L portion of the extracted DNA will be used for qPCR analysis and the remainder used for 16S rDNA amplicon generation.

#### *High-throughput metagenomics sequencing:*

Microbiome characterization will be performed by sequencing the V3-4 region of the 16S rRNA gene followed by extensive bioinformatics analysis related to microbial composition, diversity, and community structure. Microbial DNA extraction, 16S rRNA gene-based next-generation sequencing (using the Illumina MiSeq), quality filtering, and microbiome-based analysis will be performed [8]. Each sample will be amplified using a

barcoded primer, which yields a unique sequence identifier tagged onto each individual sample library. Illumina-based sequencing will yield > 15,000 reads per sample. Operational taxonomic units (OTUs) will be defined as  $\geq 99\%$  identity. To analyze differences across timepoints, the OTU table will be normalized to the lowest number of sequences per sample, then consolidated by summing to species level and to each successively higher taxonomic level. The alpha diversity parameters Chao and Shannon (based on number of OTUs) and Phylogenetic Diversity (PD) (based on phylogenetic relationships), will be generated in QIIME or R; alpha diversity is widely regarded as an indication of microbiota health. For beta diversity, which describes the relationships between samples, weighted Unifrac distance matrices will be generated in QIIME.

## 6.2 Statistical analyses

In general, the healthy volunteer analyses will assess changes in total and species-specific microbiota over time as well as changes in microbial diversity. Significance differences over time will be calculated using Mann-Whitney U test. Analyses will be performed using SAS (SAS Institute, Cary NC) or R on log-transformed data. The LEfSe (Linear Effect Size) algorithm [9] will be used to identify significant differences in microbiota composition between baseline and each study time point, followed by Wilcoxon Signed Rank tests on identified taxa. The Benjamini-Hochberg procedure will be used to control the false discovery rate at 0.10 [10]. The MaAsLin algorithm will be used to find associations of taxa with treatment. For beta diversity, principal co-ordinates analyses on weighted Unifrac distance matrices generated in QIIME will be performed in the vegan package in the statistical program R. Finally, using the methods described by Burdet et al, Shannon diversity (a measure of alpha diversity) will be compared at each time point for subjects that receive moxifloxacin or comparators[11].

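### Section 6.2 tests change over time in the same 8 participants with the independent-samples Mann-Whitney U test, which leaves total microbiota and alpha diversity without a paired test and usually costs power

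*Combined protocol and SAP*

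**What the plan says.** Section 6.2 opens with its aim: "the healthy volunteer analyses will assess changes in total and species-specific microbiota over time as well as changes in microbial diversity". The next sentence names the test: "Significance differences over time will be calculated using Mann-Whitney U test". It does not say which time points are contrasted.

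The rest of 6.2 covers other ground:

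- LEfSe is used to "identify significant differences in microbiota composition between baseline and each study time point", "followed by Wilcoxon Signed Rank tests on identified taxa". This is the only paired test named, and it applies only to taxa that LEfSe has selected.
- MaAsLin relates taxa to treatment, and principal co-ordinates analysis handles beta diversity.
- Shannon diversity "will be compared at each time point for subjects that receive moxifloxacin or comparators".
- On multiplicity: "The Benjamini-Hochberg procedure will be used to control the false discovery rate at 0.10". The tests that make up the family are not listed.

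The alpha-diversity measures are defined in section 6.1 (sequencing paragraph) as Chao, Shannon and phylogenetic diversity. The Synopsis and section 3.2 give a single group of 8 people on one regimen. Section 4.4 says: "Participants will provide a total of 13 stool samples and 12 saliva samples during study participation". One of the two Day 1 stool samples is taken before dosing.

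**The concern.** With one cohort and repeated sampling, a baseline sample and a later sample come from the same person. Mann-Whitney treats them as coming from different people. If a person's samples are positively correlated, the real variation in the difference is smaller than the test supposes. Stable differences between people then stay in the comparison as noise. False positives fall below the nominal rate, and moderate real changes are missed more often than with a paired test.

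This matters because 6.2 puts total microbiota and diversity among its main outcomes, and the objective (section 1.1.1) is to describe the drug's effect on the gut microbiome. Section 2.0 explains that the interest is in therapies that disturb the native flora little. A test that tends to miss moderate change leans towards the conclusion that little happened.

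The section is also inconsistent, since it pairs the data for selected taxa but not for the other outcomes.

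**Working it through.** **Inputs from the documents.** There are 8 participants and one regimen (Synopsis, 3.2). Each gives 13 stool samples (4.4): two on Day 1, nine on Days 2 to 10, one on Day 13 and one on Day 31. Removing the Day 1 pre-dose sample leaves 13 − 1 = 12 post-baseline samples. The false discovery rate is 0.10 (6.2). The plan gives no power figure to reproduce.

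**Assumed, because the documents are silent.** Within-person correlation r from 0 to 0.7, shifts of 0 to 2 SD on the log scale, two-sided 0.05, normal data with equal SD. The contrast is one time point against baseline, the only kind that 6.2 spells out (in the LEfSe sentence).

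**Why pairing matters.** In SD units the standard error of the mean change is √[2(1 − r)/8]. An independent-samples comparison in effect uses √(2/8) = 0.50 whatever r is. The true values are 0.50 (r=0), 0.42 (r=0.3), 0.35 (r=0.5) and 0.27 (r=0.7). For a 1 SD shift, the paired t non-centrality at r=0.5 is 1/0.354 = 2.83 on 7 df. That gives 68% power.

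**Exact null distributions.** Mann-Whitney, 8 v 8, rejects at U ≤ 13 (size 0.0499), and its smallest two-sided p is 2/12,870 = 0.00016. Signed-rank with 8 pairs rejects at W ≤ 3 (size 0.0391), and its smallest p is 2/256 = 0.0078. With 7 pairs the smallest p is 2/128 = 0.0156.

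**Simulation, 8 pairs, 100,000 trials per setting, two-sided 0.05.**

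| r | Mann-Whitney type I error | Power at 1 SD: Mann-Whitney | Signed-rank | Paired t |
|---|---|---|---|---|
| 0 | 5.0% | 44% | 35% | 41% |
| 0.3 | 2.5% | 43% | 47% | 54% |
| 0.5 | 1.2% | 44% | 61% | 68% |
| 0.7 | 0.3% | 45% | 83% | 88% |

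The paired t type I error is about 5% throughout.

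Other settings, Mann-Whitney v paired t:

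- 0.5 SD: 9% v 23% (r=0.5), 7% v 35% (r=0.7).
- 1.5 SD: 83% v 95% (r=0.5), 87% v 100% (r=0.7).
- 2 SD: 98% v 100% (r=0.5).
- 7 pairs, 1 SD: 31% v 60% (r=0.5), 31% v 81% (r=0.7).

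**If Benjamini-Hochberg covers these tests.** One index at 12 time points gives a threshold of 0.10/12 = 0.0083 for a contrast that is the only one rejected. Power at 1 SD is then 12% v 32% (r=0.5) and 11% v 55% (r=0.7). For an assumed family of 3 indices × 12 = 36 tests, the threshold is 0.10/36 = 0.0028, and power is 4% v 16% and 4% v 33%.

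**The case against.** **The loss depends on inputs the plan does not give.** This is true. Against signed-rank, the crossover lies at r of about 0.2 to 0.3, and below that Mann-Whitney is slightly better. At r = −0.3 it is anti-conservative (8.1%). If the SD doubles or halves after dosing, its type I error is about 2.4% at r=0.5 and 1.3% at r=0.7. That is less conservative than in the table but still below 5%. Positive correlation is the natural expectation for repeat samples from one person. The mismatch between test and design needs no assumed figure.

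**The Benjamini-Hochberg figures are a worst case.** They describe an isolated effect. The procedure is step-up, and ten days of antibiotic may well move several time points together. A simulation of 12 contrasts sharing one baseline (1 SD, r=0.5, 10,000 trials) gave power per shifted contrast, Mann-Whitney v paired t, of 12% v 34% with 1 shifted, 26% v 59% with 6 and 39% v 71% with 11. At 2 SD with 6 shifted it was 97% v 100%. The gap narrows for large effects but persists for moderate ones.

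**Signed-rank would be the smallest edit.** It would also be a valid correction. Its gain is smaller than that of paired t (61% v 68% at r=0.5), and its p-value floor needs stating.

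**The study is descriptive, and 6.2 borrows a published method for Shannon.** The objective carries no decision rule, and the paired data remain available, which limits the severity. The cited method could not be checked. As worded, the Shannon sentence compares drug groups, and nobody in this protocol receives moxifloxacin.

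**Conclusion.** The concern holds: the test named in 6.2 does not fit the design. As worded, total microbiota, Chao, Shannon and PD have no paired analysis against baseline. Under moderate positive correlation (r=0.5 to 0.7, assumed), a nominal 5% test runs at 1.2% to 0.3%. It finds a 1 SD shift with 44% to 45% power, where a paired t test has 68% to 88%. The loss vanishes or reverses near zero correlation, and it is negligible for 2 SD shifts at 0.05. These sizes rest on normal data with equal SD. This should be fixed, but it does not undermine the study, because the data needed for a paired analysis will be collected anyway.

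**What to change.** In 6.2, for total microbiota and alpha diversity, replace Mann-Whitney with the log-scale change at each time point from the same participant's Day 1 pre-dose stool sample. Analyse it by paired t and report the mean change with a 95% CI at each time point. State the contrasts and which tests form the Benjamini-Hochberg family.

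If signed-rank is preferred, state its floor. With 8 pairs the floor (0.0078) just clears the lone-test threshold for 12 contrasts (0.0083). One missing sample raises that contrast's floor to 0.0156, which is below the limit only if at least two of the 12 are rejected (2 × 0.10/12 = 0.0167). For 36 tests, 8 pairs need at least three rejections (3 × 0.10/36 = 0.0083).

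A mixed model with a participant effect is an option only if its covariance allows for serial correlation and for variances that differ between time points. With a random intercept and equal variances, type I error was 11% to 24% when the residual SD during treatment to Day 13 was half that at baseline and Day 31 (assumed). It was 7% to 8% with AR(1) residuals of 0.6. Paired t stayed at about 5% in both cases.

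The cost is a few sentences, with no new samples or participants. There are two downsides:

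- Some power is lost if the correlation is near zero (44% v 41% at 1 SD and 0.05; 75% v 64% at 2 SD and 0.0083).
- Paired t with 8 pairs can exceed 5% when changes are strongly skewed (10.6% for exponential changes, assumed), so individual changes should be plotted.

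### Section 6.2 tests for change over time with an unpaired test, names no lead measure or time point, and leaves the scope of the Benjamini-Hochberg correction open

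*Combined protocol and SAP*

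**What the plan says.** The only objective (section 1.1.1) is "To characterize the impact of 5 days of IV omadacycline followed by 5 days of oral omadacycline on the gut microbiome of healthy volunteers". It names no outcome measure, time point or hypothesis. Section 3.2 says "The study will enroll 8 participants" and gives no justification for the number.

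Section 4.4 says "Participants will provide a total of 13 stool samples and 12 saliva samples during study participation". Two of the stools fall on Day 1, one before and one after dosing. The others are from Days 2 to 10, Day 13 and Day 31. Section 6.1 lists Chao, Shannon and Phylogenetic Diversity as alpha-diversity measures, none ranked above the others.

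Section 6.2 covers total and species-specific microbiota as well as diversity. For the test it says "Significance differences over time will be calculated using Mann-Whitney U test", with no significance level, sidedness or contrast. A comparison of baseline with each time point is stated only for composition, through LEfSe followed by signed-rank tests on the taxa found. The next sentence says "The Benjamini-Hochberg procedure will be used to control the false discovery rate at 0.10", without naming the family of tests. Shannon is singled out once, for a comparison involving recipients of moxifloxacin or comparators. That does not make it the lead measure for change over time.

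**The concern.** A plan that will declare significance has to say for which quantity, at which time, by which test and within which family. Three of these are open for diversity: measure, time point and family. The fourth, the test, is stated but does not fit the data, because Mann-Whitney treats a person's baseline and later stool as independent samples.

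An analyst could follow section 6.2 to the letter and still choose afterwards which index and day to put forward, and whether to correct. Neither the authors nor a reader could then state the error rate of the headline result. The unpaired test also gives away power when people differ consistently from one another, which is a real cost with eight participants.

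**Working it through.** **1. Samples and contrasts.** From section 4.4: 2 (Day 1) + 9 (Days 2 to 10) + 1 (Day 13) + 1 (Day 31) = 13, which reproduces the plan's figure. One is pre-dose, so 12 are post-baseline. With three indices, 3 × 12 = 36 contrasts against baseline. This count is inferred, because section 6.2 states that contrast only for composition. All pairs of time points would give 3 × (13 × 12 / 2) = 234.

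**2. Exact properties at n = 8.** The smallest two-sided signed-rank p-value is 2/2^8 = 0.0078. The largest attainable value not above 0.05 is 10/256 = 0.039, so that is the true size of a nominal 0.05 test. For Mann-Whitney with 8 against 8, the corresponding value is 0.0499 when the samples really are independent.

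**3. Chance of any false positive among the 36.** The documents give no correlations, so these are assumed. The simulation has no true change, 8 people, 13 stools, three indices, a shared baseline stool, two-sided 0.05 and 10,000 runs per setting. Index correlation is 0.5 to 0.8, and there is no day-to-day autocorrelation beyond the within-person correlation.

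| Within-person correlation | Mann-Whitney, uncorrected | Signed-rank, uncorrected |
|---|---|---|
| 0 | 55–64% | 52–60% |
| 0.3 | 35–42% | 52–61% |
| 0.5 | 20–24% | 52–61% |
| 0.7 | about 8% | 52–60% |
| 0.8 | about 3% | 52–60% |

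Simulation error is about half a percentage point (√(0.5 × 0.5 / 10,000) = 0.005). The Mann-Whitney column falls because the test ignores the pairing: its size per test drops from 0.050 at correlation 0 to about 0.003 at 0.7.

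**4. If BH at 0.10 covers all 36.** The chance of any rejection when nothing changes is at most about 7% with Mann-Whitney and about 3% with signed-rank tests.

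**5. Can BH reject anything at n = 8?** With m signed-rank tests and k of them at the floor, BH rejects if 0.0078 ≤ 0.10 × k/m, that is k ≥ 0.078m. For m = 36 this is 2.8, so three tests suffice (0.10 × 3/36 = 0.0083). With one pair missing throughout, the floor is 2/2^7 = 0.0156 and the requirement is 5.6, so six. Taking out one lead contrast leaves 35. If total load is tested at the same 12 stools (an assumption), m = 47 and 0.078 × 47 = 3.7, so four.

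**The case against.** The objective is descriptive, the study is small, and no success criterion or power claim is made. Family-wise error under a complete null is therefore not the natural yardstick. This stands: the main harm is a headline that can be chosen afterwards, and the error rates only show how much depends on the open choices.

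The BH sentence is also not restricted to taxa. Reading it as leaving out diversity rests only on its position after the taxa step. This stands too, so the diversity tests cannot be called uncontrolled. What can be said is that their family is undefined.

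Four stronger readings are tempting, and the documents do not support them:

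- **A chance finding is likely.** That holds for uncorrected paired tests, or for Mann-Whitney with almost no within-person correlation. It fails for Mann-Whitney at moderate correlation, and for either test if BH applies.
- **The risk is 84%.** This is 1 − 0.95^36 = 0.842, which needs 36 independent tests. The contrasts share participants and a baseline stool.
- **The objective rests on 36 alpha-diversity tests.** It also draws on total and species-specific microbiota, taxa and beta diversity. That widens the choice of headline, but the 36 are not the whole basis.
- **A BH family is no remedy with eight people.** Step 5 shows that three of 36 contrasts at the floor are enough.

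**Conclusion.** The point holds as a defect of specification together with an ill-fitting test. The plan does not mark which result answers its objective, uses an unpaired test on paired data, and does not say whether BH reaches the diversity tests. Depending on how those gaps are filled, the chance of at least one false positive among the 36 inferred contrasts ranges from about 3% or less to about 64%.

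The ranges rest on the assumed correlations, a complete null, two-sided 0.05 and comparison of every later stool with baseline. The missing lead contrast, the lack of pairing and the undefined family rest on none of these. This should be corrected before analysis. It does not show that any particular finding will be false.

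**What to change.** In section 6.2, name one lead contrast. An example is the within-person change in Shannon diversity from the pre-dose Day 1 stool to one pre-specified end-of-treatment stool. Day 10 is the last dosing day, but section 4.4 takes the first stool of the day and does not place it relative to that day's dose. If Day 10 is chosen, say that the stool may precede the dose. Day 13 is the alternative. Which one matters less than fixing it in advance.

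Test this contrast once with the exact Wilcoxon signed-rank test at two-sided 0.05 and report it with a 95% confidence interval. Its true size is 0.039 with eight complete pairs. The documents give no standard deviation or effect size, so its power cannot be stated.

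Use paired tests for the other diversity and load contrasts. Place them in one stated BH family at 0.10, separate from the taxa family. Report them mainly as estimates with intervals, labelled exploratory.

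The cost is SAP wording only, with no extra samples or participants. The downside is that an isolated significant day on another index can no longer be presented as the main result.
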